Index TB patients and their household contacts will be invited to participate in this public health evaluation in accordance with guidelines of the Uganda NTLP. We believe this research meets the first condition outlined above: (1) The consent form would be the only document connecting index patients and their contacts to the results of the focus group discussions or interviews and the primary risk for the entire study is a breach of privacy. Additionally, health-worker interventions to improve the quality of care are a routine part of public health practice and do not pose a risk to the participants.

We will obtain verbal consent for qualitative data collection with index patients, contacts and community members; while the purpose of these fits with routine quality improvement, since these activities do not commonly include community members, and because we are offering compensation for time and transport, we will include verbal consent to maximize transparency.

Index TB patients, household contacts: Stepped-Wedge Trial Contact Investigation

According to 45 CFR 46.116(f)3, effective 19 July 2018, investigators may ask an IRB to approve a waiver of informed consent if several conditions are met. We list these criteria in bold below, accompanied by explanations of how and why they apply to the proposed study:

- i. **The research involves no more than minimal risk to the subjects.** All participants will be offered standard contact investigation procedures, and the additional services provided during the intervention phase of the study do not pose any additional risks beyond those encountered in everyday life.
- ii. **The research could not practicably be carried out without the waiver or alteration.** It is not practical for community health workers to obtain informed consent during the process of routine care. In addition, informed consent procedures change the care context for participants in ways that may reasonably alter their behavior. For these reasons, including consent procedures could compromise the scientific validity of the study which seeks to identify best strategies for implementation under real-world conditions.
- iii. **The research could not practicably be carried out without using identifiable private information.** Collection of name, age, telephone number, residence, information about health status and other personal health information is required to carry out TB contact investigation according to existing Uganda public health guidelines. It is not possible to evaluate the implementation of these services without collection of this information.
- iv. **The waiver or alteration will not adversely affect the rights and welfare of the subjects.** The rights of patients to accept or decline care are similar to their rights in everyday medical practice and are not altered by the research.
- v. **When appropriate, the subjects will be provided with additional pertinent information after participation.** All pertinent results of TB evaluation will be communicated to patients via routine or enhanced processes of care.

7. **Evaluation of Subject(s) Capacity to Provide Informed Consent/Assent:** Indicate how the personnel obtaining consent will assess the potential subject's ability and capacity to consent to the research being proposed. We will be requesting a waiver of consent for data collection activities related to health workers opinions and actions in delivering contact investigation. However, as is done in routine medical settings, community

health workers will obtain permission before conducting routine TB evaluation services. Health workers participating in study related activities will be informed that they can choose at any time to end participation or not answer any question that they do not feel comfortable answering.

Research staff with human subjects protection training will assess whether individuals have capacity to provide verbal consent based on appropriate answers to questions about the purpose of the procedures (i.e. to get information to improve services for community members) and their affirmation to participate.

8. Non-English Speaking Subjects: Explain provisions in place to ensure comprehension for research involving non-English speaking subjects. If enrollment of these subjects is anticipated, translated copies of all consent materials must be submitted for approval prior to use.

All health workers speak both English and Luganda, the most common local language spoken. Health workers will converse with index TB patients and household contacts in the language of their preference as is done in the health facilities. We will not recruit those who do not speak English or Luganda for qualitative data collection.

As a limited alternative to the above requirement, will you use the short form* for consenting process if you unexpectedly encounter a non-English speaking individual interested in study participation and the translation of the long form is not possible prior to intended enrollment? **N/A** YES NO

Note* If more than 2 study participants are enrolled using a short form translated into the same language, then the full consent form should be translated into that language for use the next time a subject speaking that language is to be enrolled.

Several translated short form templates are available on the HRPP website (yale.edu/hrpp) and translated HIPAA Research Authorization Forms are available on the HIPAA website (hipaa.yale.edu). If the translation of the short form is not available on our website, then the translated short form needs to be submitted to the IRB office for approval via modification prior to enrolling the subject. *Please review the guidance and presentation on use of the short form available on the HRPP website.*

If using a short form without a translated HIPAA Research Authorization Form, please request a HIPAA waiver in the section above.

9. Consent Waiver: In certain circumstances, the HIC may grant a waiver of signed consent, or a full waiver of consent, depending on the study. If you will request either a waiver of consent, or a waiver of signed consent for this study, complete the appropriate section below.

Not Requesting any consent waivers

Requesting a waiver of signed consent:

- Recruitment/Screening only (if for recruitment, the questions in the box below will apply to recruitment activities only)
- Entire Study (Note that an information sheet may be required.)

For a waiver of signed consent, address the following:

- Would the signed consent form be the only record linking the subject and the research? YES NO
- Does a breach of confidentiality constitute the principal risk to subjects? YES NO

OR

- Does the research pose greater than minimal risk? YES NO
- Does the research include any activities that would require signed consent in a non-research context? YES NO

We are working on quality improvement proceedings and no data collected is outside of routine public health proceedings for community health workers. For index, contact participants and community members, we will obtain verbal consent for interviews or focus group discussions. Signed consent would be the only record linking these participants to the research and the breach of confidentiality is the principal risk to subjects.

 Requesting a waiver of consent:

- Recruitment/Screening only** (if for recruitment, the questions in the box below will apply to recruitment activities only)
- Entire Study**

For a full waiver of consent, please address all of the following:

- Does the research pose greater than minimal risk to subjects?
 - Yes *If you answered yes, stop. A waiver cannot be granted.*
 - No
- Will the waiver adversely affect subjects' rights and welfare? YES NO
- Why would the research be impracticable to conduct without the waiver?
- Where appropriate, how will pertinent information be returned to, or shared with subjects at a later date?

SECTION IV: PROTECTION OF RESEARCH SUBJECTS**Confidentiality & Security of Data:**

1. What protected health information (medical information along with the HIPAA identifiers) about subjects will be collected and used for the research? We will collect the following information:
 - Names
 - Dates
 - Postal addresses
 - Phone numbers
 - Medical record numbers
2. How will the research data be collected, recorded and stored? All data will be collected using mobile tablets equipped with a customized survey software application such as a CommCare (Dimagi, Cambridge, MA) or RedCap application. Quantitative data will temporarily be stored on these devices during collection but will then be uploaded via a 3G connection to a remote, cloud-based, encrypted server. We will ensure that all safety features have been reviewed and approved by an independent security expert. Data on the server will be password protected. Only study staff will have access to identifiable data collected. As many journals now require a data repository in order to publish findings, we will de-identify all data at the earliest possible moment

after trial completion and subsequently create a de-identified data repository using one. We will have at least 2 study team members verify that the dataset is completely de-identified and that there exists no way of connecting the data to individual participants prior to submitting the data to a data repository. No one outside of the study team will have access at any point to identifiable data.

Qualitative data in the form of digital recordings and written transcripts will be stored on password protected cloud-based servers and backed up on secured institutional servers. Recordings will be carefully destroyed once transcriptions have been completed. Transcription will be conducted by professional transcribers with signed NDA's and confidentiality agreements. English transcripts may be transcribed by a verified transcription service such as Rev or similar transcription service that protects participant confidentiality while producing quality transcriptions. We will create a data repository for qualitative data as well however, as transcripts pose a greater challenge in de-identification due to people referencing specific individuals or places throughout their interview that may be used to identify that participant, we will only do this upon request by a journal for publication and only if possible to completely de-identify the transcripts. We may submit a limited subset of the transcripts instead of the full transcripts to ensure that re-identification is impossible. We will only submit transcripts if at least 2 study team members have verified that all transcripts, or parts of transcripts if only a subset of the data is to be kept in a repository, are completely de-identified and there exists no way to re-identify participants. No one outside of the study team will have access to identifiable data including the original audio recordings and the raw transcripts produced from these recordings.

3. How will the digital data be stored? CD DVD Flash Drive Portable Hard Drive Secured Server Laptop Computer Desktop Computer Other: Cloud-based Servers
4. What methods and procedures will be used to safeguard the confidentiality and security of the identifiable study data and the storage media indicated above during and after the subject's participation in the study? *All data will be stored on encrypted servers with password protection. Only approved study staff will have access to data collected.*

All portable devices must contain encryption software, per University Policy 5100. If there is a technical reason a device cannot be encrypted please submit an exception request to the Information Security, Policy and Compliance Office by clicking on url <http://its.yale.edu/egrc> or email [contact]

5. What will be done with the data when the research is completed? Are there plans to destroy the identifiable data? If yes, describe how, by whom and when identifiers will be destroyed. If no, describe how the data and/or identifiers will be secured.

All data will be stored securely on password protected servers. Data will be de-identified once enrollments are complete and the personal health identifiers destroyed under the direction of the principal investigator.

6. If appropriate, has a Certificate of Confidentiality been obtained? **N/A**

SECTION V: POTENTIAL BENEFITS

Potential Benefits: Identify any benefits that may be reasonably expected to result from the research, either to the subject(s) or to society at large. (Payment of subjects is not considered a benefit in this context of the risk benefit assessment.)

Health workers may gain additional satisfaction from participating in research and helping to generate new knowledge to improve care and from delivering better quality care. Indirectly, the study may benefit future TB

patients, their households, and health workers involved on contact investigation for TB by improving the quality of TB contact investigation and evaluation.

SECTION VI: RESEARCH ALTERNATIVES AND ECONOMIC CONSIDERATIONS

1. **Alternatives:** What other alternatives are available to the study subjects outside of the research?
The only alternative would be to decline participation.
2. **Payments for Participation (Economic Considerations):** Describe any payments that will be made to subjects, the amount and schedule of payments, and the conditions for receiving this compensation.
We will provide appropriate compensation for health workers, community health riders, contacts and index patients participating in qualitative data collection activities designed for quality improvement and evaluation of contact tracing implementation. Health workers, community health riders, community members, index patients and their contacts who participate in the focus group discussions and/or interviews or surveys outside of routine health data collection (e.g. CHW and CHR surveys on psychological safety) may be compensated a small amount of money (~20,000 Ugandan shillings, equivalent of ~\$5.66USD) for their time and/or transportation reimbursement. As costs have risen due to the pandemic, the stated amount is more appropriate than what has been used pre-pandemic (increase of ~10,000 UGX).
3. **Costs for Participation (Economic Considerations):** Clearly describe the subject's costs associated with participation in the research, and the interventions or procedures of the study that will be provided at no cost to subjects.
Study participants will not be charged for participation.
4. **In Case of Injury:** This section is required for any research involving more than minimal risk, and for minimal risk research that presents the potential for physical harm (e.g., research involving blood draws).

All participants will be offered standard TB contact investigation procedures and the additional services provided during the intervention phase of the study do not pose any additional risks beyond those encountered in everyday life. Therefore, this section is N/A due to the minimal risk posed.

- a. Will medical treatment be available if research-related injury occurs? *Write here*
- b. Where and from whom may treatment be obtained? *Write here*
- c. Are there any limits to the treatment being provided? *Write here*
- d. Who will pay for this treatment? *Write here*
- e. How will the medical treatment be accessed by subjects? *Write here*

IMPORTANT REMINDERS

Will this study have a billable service? Yes No

Are there any procedures involved in this protocol that will be performed at YNHH or one of its affiliated entities?
Yes No

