Community health workers in twelve clinics will identify at least 588 symptomatic contacts (*i.e.* possible TB patients) among 1764 household and close contacts in approximately 2304 eligible index patient clusters over a 16-month period, or up to 7 contacts needing evaluation for TB per referring clinic during each two-month block. With this sample size, assuming a clinic intra-cluster correlation coefficient (ICC) of 0.043 and within-index- patient-cluster ICC of 0.7, and accounting for covariates, we will have 83% power to detect a 15% or greater increase in the proportion completing evaluation from 20% to 35%, at alpha of 0.05, following crossover to the intervention. These estimates account for the proposed stepped-wedge design with 6 steps and a one-step transition period (*i.e.*, an “incomplete” design) at each site. Sample size estimates were reached using PASS 15 and Stata 14, with an extension to account for multiple levels of clustering as per Hemming et al. because index patients and contacts are participants in routine services, and the design of a stepped wedge trial has a fixed duration, we will not limit enrollment if it exceeds these numbers, which may be up to four-fold higher in some or all sites, or more if the intervention strategy is highly effective. For example, if up to 1932 symptomatic contacts, or 23 contacts needing evaluation for TB per referring clinic are identified during each two-month block, we would have 91% power to detect a 10% or greater proportion increase in the proportion completing evaluation from 20% to 30%, at alpha of 0.05, assuming the above noted ICCs.

Evaluation of the fidelity of the intervention strategy

We will propose parallel convergent mixed-methods studies involving quantitative assessments of the fidelity of the implementation strategy and its behavioral mechanisms, using validated psychosocial scales, and we will assess other aspects of fidelity, adaptation, and context through qualitative studies involving interviews and focus group discussions with cases, contacts, community health workers, and community health riders.

However, prior to that, we describe our plans in this protocol to validate quantitative study instruments.

Quantitative studies

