If we power for a minimum detectable difference of 0.20, a sample of 12 clinics/clusters in a complete stepped-wedge cluster-randomized design with 7 time periods (including the baseline), 6 steps, 2 clusters switching from pre-intervention (control) to post-intervention (treatment) at each step, two levels of ICC (rho-alpha of 0.172 and rho-beta of 0.647 from our pre-trial data), an average of 11 index TB patients per cluster per 2-months' time period, a minimum of 1 symptomatic contact per index TB patient, a total number of index TB patients needed for the trial is 924 which achieves 99% power for a minimum detectable proportion difference of 0.1 between a pre-intervention proportion of 0.2 and a post-intervention proportion of 0.4.

These and other sample size estimates are indicated under Scenario 1 in Table 2, in the upper panel in bold, black font.

We also are proposing sample size calculations for other contingencies. Specifically, we wish to plan for scenarios in which one or both sites in a paired-site cluster do not achieve the expected number of symptomatic contacts patients due to secular events, the whole pair will be excluded from the final analysis. Given the effect of a small number of clusters on the power of SWTs, we see two plausible scenarios namely:

- i. Scenario 2: One pair of clusters is excluded from the final analysis. In this case, the number of steps reduces to 5, the time periods reduce to 6 and the number of clusters reduces to 10. The power estimates for this scenario are presented in Table 2 above, in the middle panel in blue ink.
- ii. Scenario 3: Two pairs of clusters are excluded from the final analysis. In this case, the number of steps reduces to 4, the time periods reduce to 5 and the number of clusters reduces to 8. The power estimates for this scenario are presented in Table 2 above, in the lower panel in purple ink. This is the worst-case scenario. The estimates indicate that this scenario would have 99.8% for a minimum detectable proportion difference of 0.2 between a pre-intervention proportion of 0.2 and a post-intervention proportion of 0.4.

Blinding

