This sequence of allocation restricted by sites will be determined through a two-stage random drawing during a public randomization ceremony held in Kampala, Uganda. A senior clinician representative of each health center (e.g., the TB focal person), the Health Facility Administrator-in-Charge, and the District Health Officer will be invited to attend a public randomization ceremony chaired by the Uganda NTLP Director. In the first, so-called “Cluster Stage”, health facilities will be divided into high-volume and low-volume strata for cluster assignments. Each health center representative will draw, without replacement, one ball labeled with the cluster designation, until all sites are assigned in paired clusters. In the second and final, or “Group Stage,” the two representatives of each cluster will assign one representative to draw, without replacement, 1 of 6 balls (labeled 1, 2, 3, 4, 5, 6) from an opaque bag to choose the group. Group 1 will be the first group to cross over, Group 2 the second to cross over, and so on. The sites will follow this cross-over sequence at equally spaced, 2-month intervals during the trial period, starting at the beginning of month 3.

Statistical Methods

For standardization purposes, the start of effective intervention exposure for clusters will be considered the first Monday of the next calendar week after the end of each 8-week transition period. This standardization will help fix the trial period slices and improve statistical efficiency for the within-period analyses. We will use a cluster-period mixed-effects logit model[5, 6] to assess differences between post-intervention and pre-intervention periods with regard to the proportion of contacts who completed TB evaluation within 60 days of index treatment initiation, the proportion of contacts diagnosed with active TB, the proportion of contacts initiating TB preventative therapy and proportion of all TB cases among contacts. We will use a cluster-period mixed-effects Poisson model[5, 6] to assess the difference between post-intervention and pre-intervention periods with regard to the count of contacts diagnosed with active TB and the count of contacts initiated on TB preventative therapy within and between periods. We will test for secular trends using both fixed and random effects. If secular trends are present, we will use a segmented regression model.

a. Dataset assembly, cleaning, and creation of new variables

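### The protocol's 83% and 91% power are not delivered by its stated inputs: with both proportions' variances they are about 74–76% and 86–87% on a complete layout, and about 60% and 73% with the transition block removed

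*Protocol*

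**What the plan says.** The Sample Size paragraph of the protocol makes two power claims.

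- **Rise from 20% to 35%.** "Community health workers in twelve clinics will identify at least 588 symptomatic contacts", or "up to 7 contacts needing evaluation for TB per referring clinic during each two-month block", and with that number "we will have 83% power to detect a 15% or greater increase in the proportion completing evaluation from 20% to 35" per cent.
- **Rise from 20% to 30%.** "if up to 1932 symptomatic contacts, or 23 contacts needing evaluation for TB per referring clinic are identified during each two-month block", then "we would have 91% power to detect a 10% or greater proportion increase in the proportion completing evaluation from 20% to 30" per cent.

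Both are made "assuming a clinic intra-cluster correlation coefficient (ICC) of 0.043", an index-patient ICC of 0.7 and alpha 0.05. The paragraph says that covariates were accounted for but gives no size for their effect. It also says that the estimates allow for six steps and a one-step transition at each site, that is, an incomplete design. It does not say which binomial variance was used, and it does not state sidedness. The SAP (Power and sample size calculation) specifies a two-sided Wald Z-test.

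For the analysis, the SAP (Statistical Methods) says "We will use a cluster-period mixed-effects logit model". Its Intervention Effect Analysis section then moves to a log-link Poisson model for proportions above 15%.

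**The concern.** For a yes/no outcome the variance is fixed by the proportion. The protocol's own targets give 0.16 under control, and 0.2275 (42% larger) or 0.21 (31% larger) under intervention. A power claimed for a rise from 20% to 35% should use the larger variance in intervention cells. If 0.16 is used everywhere, intervention data are treated as less variable than the target itself implies, and power is overstated. At stake is whether the protocol's power for 20% to 35% clears 80%. This is separate from the transition block: correcting only the layout would leave the restated figures about 6 to 8 points too high.

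**Working it through.** **Inputs.** From the protocol: 12 clinics, 2 crossing per step, 6 steps, clinic ICC ρ = 0.043, n = 7 or 23 symptomatic contacts per clinic-block. From the SAP: two-sided Wald z at 5%. The index-patient ICC of 0.7 is taken to have no effect, which is exact with one symptomatic contact per index patient. The protocol's 588 such contacts among about 2304 index patients average below one (588/2304 = 0.26).

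**Layout.** Both totals fit seven blocks of data per clinic: 7 × 12 × 7 = 588 and 23 × 12 × 7 = 1932. The counts alone do not settle the layout. Eight two-month blocks (the stated 16 months) with one removed per clinic also leave seven.

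**Formula.** Fixed period effects and a random clinic intercept, with cell variance s = σ²(1−ρ)/n and clinic variance τ² = ρσ²:

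Var(θ) = K·s·(s + Tτ²) / [(KU − W)s + (U² + KTU − TW − KV)τ²], and power = Φ(Δ/SE − 1.96).

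For the complete layout K = 12, T = 7, U = 42, W = 364 and V = 182. So KU − W = 140, and the second coefficient is 1764 + 3528 − 2548 − 2184 = 560.

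**Reproducing the printed figures, σ² = 0.16 in every cell.** τ² = 0.043 × 0.16 = 0.00688.

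- n = 7: s = 0.16 × 0.957/7 = 0.02187. Var = 12 × 0.02187 × 0.07003 / (3.062 + 3.853) = 0.002658, SE = 0.0516, z = 0.15/0.0516 = 2.91, power **82.9%** (printed 83%).
- n = 23: s = 0.16 × 0.957/23 = 0.006657. Var = 12 × 0.006657 × 0.05482 / (0.932 + 3.853) = 0.000915, SE = 0.0303, z = 0.10/0.0303 = 3.31, power **91.1%** (printed 91%).

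**Using both proportions' variances, same layout.** With one common variance the SE scales with its square root.

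- Average of the two variances, 20% to 35%: (0.16 + 0.2275)/2 = 0.19375. SE = 0.05156 × √(0.19375/0.16) = 0.0567, z = 2.64.
- Average of the two variances, 20% to 30%: (0.16 + 0.21)/2 = 0.185. SE = 0.03025 × √(0.185/0.16) = 0.0325, z = 3.07.
- Variance at the mean proportion: 0.275 × 0.725 = 0.1994 and 0.25 × 0.75 = 0.1875, scaled in the same way.
- Arm-specific: each cell takes its own variance and the same model is solved by generalised least squares.

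| Complete layout, 7 periods | 20% to 35%, n = 7 | 20% to 30%, n = 23 |
|---|---|---|
| Control variance throughout | 82.9% | 91.1% |
| Arm-specific | 75.7% | 87.0% |
| Average of the two | 75.3% | 86.7% |
| Mean proportion | 74.1% | 86.3% |

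**Transition block removed, 8 periods.** The same model gives 68.2% and 79.2% with control variance throughout, and 60.3% and 73.5% with arm-specific variances.

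**How far covariates could go.** With both variances on the complete layout, removing 75% of the clinic variance and none of the residual variance gives 82.8% and 91.2%. With the transition block removed, taking away all the clinic variance brings the power for 20% to 35% only to about 74%.

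**SAP Table 2.** The four 8-clinic rows print 0.9983, 1.0000, 0.9948 and 0.9999. Control variance gives 0.9983, 1.0000, 0.9946 and 0.9999 when the index-patient correlation is treated as persisting across periods. The averaged variance gives 0.9919, 0.9997, 0.9870 and 0.9994.

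**The case against.** **The variance is inferred, not stated.** A reader might conclude that the printed figures can come only from the control variance, or that no single covariate gain could give both. The documents do not support that. The level of the covariate effect is left open, and the SAP's adjusted analyses list clinic-level covariates. The 75% reduction shown above meets both figures to rounding. A one-sided test with the mean-proportion variance also comes near (83.2% and 92.0%), though it does not match both and the SAP's test is two-sided. What remains is that the covariate route needs a large unstated gain and the complete layout that the protocol says it did not use.

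**The planned model is not linear.** This is fair. One might argue that a logit model must lose power in the same way because its information depends on the intervention proportion's p(1−p). That argument runs the wrong way: on the log-odds scale a larger p(1−p) means more information. A simulated mixed-effects logit analysis (1500 runs per case) nevertheless gave similar levels: 74.9% and 85.6% complete, 59.5% and 73.7% with the transition removed. The log-link Poisson model, which the SAP's 15% rule would bring in for proportions of 20% to 35%, was not simulated.

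**The SAP supersedes the protocol.** This stands and limits the consequence. The SAP Introduction gives the SAP precedence, and its sample size uses other ICCs, effects and numbers. Its printed command uses 0.4 to 0.6, where 0.4 × 0.6 = 0.6 × 0.4 = 0.24, so the choice of arm variance has no effect. A reader might infer from Table 2 that the SAP's power fails too, for example where it says of its two-pairs-lost scenario "The estimates indicate that this scenario would have 99.8% for a minimum detectable proportion difference of 0.2". On the SAP's own formula the effect is about 1 point or less.

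**Enrolment may exceed 588.** It may, and power would then be higher. That does not make 83% right for 588.

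**Conclusion.** The point holds for the protocol's stated power. Without a covariate gain, its inputs give about 74–76% rather than 83%, and 86–87% rather than 91%, on a complete layout. In the incomplete design that the paragraph describes, they give about 60% and 73% over eight periods. There, 83% is not reached even if covariates removed all clinic variance with the residual variance unchanged. Control variance in every cell is the simplest explanation of the printed figures, but it is not demonstrated.

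These results assume a two-sided test, fixed period effects, a clinic random intercept at ICC 0.043, and an index-patient ICC that has no effect. The finding does not show that the trial is underpowered at its actual enrolment, and it does not overturn the SAP's calculation.

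**What to change.** In the protocol's Sample Size paragraph, recompute both powers with p1(1−p1) in control cells and p2(1−p2) in intervention cells, on the incomplete layout that the paragraph describes. Alternatively, simulate the planned primary analysis, including the log-link Poisson model for proportions above 15%. Print the restated powers, the layout, the sidedness and the variance used. Give any covariate gain as a number, and say whether it applies to clinic or residual variance. Power at the expected enrolment can be printed alongside. If SAP Table 2 is re-run, use the same variance convention.

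The cost is one re-run and a change of wording, with less favourable figures in print. Enrolment, number of clinics and analysis stay as they are.
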